3.6. Subject Replacement

Subjects who drop out will be replaced by recruitment from the SCI clinic and asking for informed consent from those who meet the I/E criteria.

4. TRIAL SCHEDULE

Table 2. Timeline of protocol per subject

Weeks in Study Protocol

| Activities | 0 | W1 | W2 | W3 | W4 |
|--|---|---------|----|----|----|
| Clinic Enrolment: | | | | | |
| Eligibility screen | X | | | | |
| Informed Consent | X | | | | |
| Incontinence Questionnaire (I-QOL) | X | | | | |
| Side effect questionnaire | X | | | | |
| TTNS demonstration | X | | | | |
| Home | | | | | |
| Bladder diary | | □-----□ | | | |
| I-QOL | | | X | | X |
| TTNS | | □-----□ | | | |
| Discontinue bladder medication | | | X | | |
| Side effect questionnaire/ TTNS survey | | | | | X |

5. STUDY DESIGN (Table 2)

Anticipated number of patients to screen: 40

- Anticipated number of patient to enrol: 20
- Anticipated drop out or loss to follow-up: 4

Approximate time to complete study recruitment: 1 year

Expected duration of subject participation: 4 weeks

TTNS protocol: (please refer to protocol HSC-MS-15-0806) electrodes 2 inch by 2 inch will be placed according to anatomic landmarks, with the negative electrode behind the internal malleolus and the positive electrode 10cm superior to the negative electrode, verified with rhythmic flexion of the toes secondary to stimulation of the flexor digitorum and hallicus brevis. The intensity level will be set to the amperage immediately under the threshold for motor contraction. If there is not contraction seen, maximal tolerable intensity will be used. In addition, if the patient perceives pain, the intensity will be lowered until comfortable. Stimulation frequency of 10 Hz and pulse width of 200ms in continuous mode will be used.^{13, 14}

- Information gathered:
 - o Clinical demographics, morbidity, and Neurologic Exam findings from interview with subjects, exam, and EMR review.

- Bladder diary will include:
 - use of TTNS with amperage and presence of toe flexion, and pain score 0-10
 - log of catheterization, volumes
 - log of incontinence episodes
 - Description of other observed changes, including but not limited to: fatigue, vision changes, mental status, bowel program changes, and sexual function changes.
- Information will be tabulated on an Excel spreadsheet on my personal work desktop, password protected. Any paper data (bladder diary) will be de-identified and retained in a locked drawer in the locked office of the PI.

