d. Rationale for Study Design

Based on our current inpatient experience, we believe this protocol can be performed safely at home by subjects and/or their caregivers if given detailed instructions. Subjects who perform intermittent catheterization are being selected because they more likely to have incontinence

than those with an indwelling catheter. If patients are interested, we will trial stimulation in clinic. We will exclude those who we cannot produce toe flexion with posterior tibial nerve stimulation. After 1 week of home stimulation, those that are on bladder medicine will discontinue the medication. There is no other harm from rapid discontinuation of bladder medication, except for incontinence. We expect that incontinence will be reduced from this first week of TTNS. The I-QOL questionnaire is administered at baseline, and at the end of 2 and 4 weeks to determine when best effects of TTNS are achieved.

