5.1. Summary of Study Design

In Specific Aim 1, we will monitor for safety, feasibility, and compliance of a home TTNS program for bladder management. In Specific Aim 2, the efficacy of home TTNS will be compared to baseline Incontinence- Quality of Life questionnaire. A bladder diary will also capture important information such as frequency and volume of catheterization, incontinence episodes, and other related observations.

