6.2. Randomization and Blinding

- a. Not Applicable.

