6.4. Study Visits and Procedures

- *Screening Visits and Procedures*

Screening will be performed in the SCI clinic by the PI and co-I SCI attendings.

Those that meet the I/E criteria will be approached for the study by the PI and co-I attendings. They have until the study period is complete to decide whether they want to participate. However, they will have to return to clinic to have the TTNS trial performed and the directions for home use.

- *Study Visits and Procedures*

Subjects will have their first study visit after their normal clinic visit. Once consented, we will trial TTNS for a response of toe flexion. If they have a response, they will be included in the study. If no response or not tolerating electric stimulation, they will not be included in the study.

Participants will have direction in clinic on the use of the Stambil+, including written, oral, and smartphone images/video if they have access.

The electric stimulation protocol will use stimulation frequency of 10 Hz and pulse width of 200ms in continuous mode for 30 minutes daily, beginning as soon as possible. For sexually active women of child-bearing age, the home use will begin after the results of a pregnancy test are provided. The goal is daily use of TTNS for 4 weeks.

Subjects will be called weekly to capture the information from the bladder diary log and to monitor progress of protocol. They will also be reminded to change electrodes weekly.

- *Final Study Visit:*

Upon completion of the 4-week protocol, subjects will return with the stimulator and the bladder diary.

- *Post Study Follow up and Procedures*

The data will be statistically analysed in the post-study follow up. Subject participation is not required.

- *Discontinuation Visit and Procedures*

If withdrawal occurs, no evaluation will be required for the final study visit, regardless of the withdrawal reason. There are no safety risks in withdrawing from this study at any point.

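### The only baseline I-QOL and side-effect questionnaires are scheduled in clinic and all follow-ups at home, so any effect of setting or mode is added to the change from baseline

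*Combined protocol and SAP*

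**What the plan says.** Table 2 in section 4 has two blocks. The Clinic Enrolment block, at week 0, holds the eligibility screen, consent, the TTNS demonstration and the two baseline questionnaires: "Incontinence Questionnaire (I-QOL) | X" and "Side effect questionnaire | X". The Home block holds I-QOL at weeks 2 and 4 and, at week 4, the row "Side effect questionnaire/ TTNS survey". No questionnaire is scheduled at home before treatment, and none is scheduled in clinic after it.

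The text gives timing but neither place nor mode. Section 1.2 d says "The I-QOL questionnaire is administered at baseline, and at the end of 2 and 4 weeks". Section 6.4 says "Subjects will be called weekly to capture the information from the bladder diary log and to monitor progress of protocol", without mentioning questionnaires. For the final study visit it says "Upon completion of the 4-week protocol, subjects will return with the stimulator and the bladder diary", again with no questionnaire.

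On the comparison, section 5.1 says "the efficacy of home TTNS will be compared to baseline Incontinence- Quality of Life questionnaire". The entry for randomization and blinding (section 6.2) is "Not Applicable". Section 11.2 compares later results with baseline by paired or repeated-measures methods and describes the study as exploratory. Section 2.4 states that the study is not powered for I-QOL and that its results are to supply the effect size for a larger trial.

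**The concern.** I-QOL and the side-effect questionnaire are subjective. Answers may differ between a clinic visit, where the subject has just consented and is being shown a new treatment, and the subject's home two or four weeks later. As scheduled, that difference in circumstances falls on the before-after contrast for every subject. A control arm measured in the same way would cancel it, but there is none.

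What is at stake is the pilot's I-QOL estimate. Nobody will rely on a significance test here, but the estimated change is meant to feed the sample size of the next trial. A shift caused by setting would go into that number and could not be removed afterwards. The side-effect contrast (Hypothesis 2.3) is exposed in the same way. The bladder diary is not, because Table 2 shows it only in the Home block.

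**Working it through.** **1. Alignment of setting and period (Table 2).**

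| Assessment | Week 0 | Week 2 | Week 4 |
|---|---|---|---|
| I-QOL | Clinic block | Home block | Home block |
| Side-effect questionnaire | Clinic block | not scheduled | Home block |

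Write the observed mean change as δ + s, where δ is everything else that changes after baseline, including any treatment effect, and s is the mean shift from the change of setting or mode. If every baseline is taken in one setting and every follow-up in the other, the data contain only the sum. A larger sample or a different test in section 11.2 does not separate the two; only the schedule can.

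**2. Is there a figure in the plan to reproduce?** No. The plan gives no I-QOL standard deviation, effect size or power. The one relevant count is in section 5: 20 enrolled and 4 expected to drop out, so 20 − 4 = 16 completers. Section 11.1 regards 14 as sufficient.

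**3. Illustration of what a pure setting shift would do.** The assumptions, none of them from the documents, are: δ = 0; a shift s of 0.1, 0.2 or 0.3 SD of the score; equal SDs before and after; a baseline-to-follow-up correlation r of 0.5 or 0.7; and a two-sided 5% paired t test.

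- SD of the change, in SD units: √(2(1 − r)). This is 1.000 for r = 0.5 and 0.775 for r = 0.7.
- Noncentrality: s / (SD of change / √n). For s = 0.2 and n = 16 this is 0.2 × 4 / 1.000 = 0.80 at r = 0.5, and 0.2 × 4 / 0.775 = 1.03 at r = 0.7.
- Rejection probability: both tails of the noncentral t with n − 1 degrees of freedom (critical value 2.131 for 15 df, 2.160 for 13 df).

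| Shift s | n = 16, r = 0.5 | n = 16, r = 0.7 | n = 14, r = 0.5 |
|---|---|---|---|
| 0 | 5.0% | 5.0% | 5.0% |
| 0.1 SD | 6.6% | 7.7% | 6.4% |
| 0.2 SD | 11.6% | 16.2% | 10.7% |
| 0.3 SD | 20.3% | 30.6% | 18.0% |

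At 0.1 SD the effect is slight; at 0.3 SD it is not. The table takes the shift to be in the direction of improvement. A shift the other way would hide a benefit.

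**4. Consequence for the next trial.** Required sample size varies with 1/(effect size)². If, for illustration, a true change of 0.3 SD were read as 0.5 SD, the next trial would be too small by a factor of (0.5/0.3)² = 2.8.

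**The case against.** **More may be read into the schedule than it says.** A reader might infer that staff administer the baseline forms and that subjects complete the later ones alone. The documents do not support this: no section says who administers any questionnaire or by what mode, in clinic or at home. If one self-completed form is used throughout, only the location changes. The case report form and study schedule listed as appendices are not in the text supplied and may settle the matter. This objection stands. What is documented is a change of scheduled place.

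**The week-4 forms may be completed in clinic.** Table 2 has no block for the final visit, so Home may simply label everything after enrolment. Subjects return at the end of week 4 (section 6.4) and could complete the forms then. It would therefore be too strong to say that no follow-up score is taken in clinic. This stands too, and it matters most for side effects, which have only the week-4 follow-up. Week 2 has no clinic visit, so that I-QOL is away from clinic on any reading.

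**The magnitude is assumed.** Correct. The shift and the correlations have no source in the documents, and the same calculation could be made for any bias in any single-arm study. The 16 completers also ignore section 3.6, under which dropouts are replaced.

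**Larger confounders remain.** There is no control arm and no blinding, regression to the mean is possible, and subjects on bladder medication stop it during the study, which bears directly on the side-effect contrast. Matching the setting removes none of these. That limits the weight of the point without answering it: those features belong to the chosen design, whereas the change of setting can be avoided by wording.

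**Conclusion.** The concern holds in a limited form. Table 2 schedules the only baseline I-QOL and side-effect questionnaires in clinic and the follow-ups at home, and no section contradicts it. With one unblinded arm and a comparison with baseline, any effect of setting or mode is added in full to the estimated change and cannot be separated from it.

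A reader might go on to conclude that the I-QOL result will be biased upwards, or that the trial's main conclusions are at risk. The documents support neither. The size and direction of any shift are unknown, and the rejection rates show only what an assumed shift would do. The primary safety and feasibility criteria do not use these before-after contrasts. What is affected is the exploratory I-QOL effect size intended for the next trial and the side-effect contrast, each of which carries other before-after confounders as well. The change is worth making because it is cheap before enrolment and the bias cannot be corrected afterwards.

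**What to change.** Amend Table 2 so that I-QOL at baseline, week 2 and week 4, and the side-effect questionnaire at baseline and week 4, all use the same mode, place and administrator, and state all three in the protocol. One workable form is the same scripted telephone administration with the subject at home, by the research assistant who already makes the weekly calls (section 6). Complete the baseline after consent and before the first home TTNS session, and the week-4 forms before the return visit.

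Two alternatives work less well. Having the subject complete the baseline form alone in clinic keeps the clinic/home split. Relying on unaided self-completion may not suit subjects with tetraplegia, whom section 3.2 expects to be unlikely to be able to sign.

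The cost is small: the instruments and the number of administrations stay the same, with one extra call for the baseline. There may be a short wait before the first home session, which has to be reconciled with the wish in section 6.4 to begin promptly. The baseline would also follow the in-clinic demonstration, so any expectation raised there would already be present when it is taken.

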3.2. Criteria for Recruitment

- Initial screening will be performed in the clinic with the subject and PI
- In those interested, they will be given an IRB-approved consent form to review and to sign.
- Those with tetraplegia will unlikely have the ability to sign and we will have a 3rd party attest to the consent.
- Patients will ideally decide to participate in clinic, but can always decide at a later date and return to clinic to trial the TTNS as part of the I/E criteria.

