3.3. Inclusion Criteria (table 1)

Table 1. Inclusion/ Exclusion Criteria

| Inclusion | Exclusion |
|------------------|---|
| 18-65 years old | Multiple medications for the bladder Cancer in the tibial nerve path and/or bladder. |

| | | |
|---|---|--|
| Neurologically stable SCI for ≥ 6 months | Other diagnoses to explain incontinence (ex: UTI, bladder stones, multiple sclerosis, etc.) | Inability to elicit toe/plantar flexion with electric stimulation during clinic visit. |
| Intermittent catheterization to empty bladder | 2+ pitting edema that does not resolve | Inability to understand directions |
| Stable bladder medications for ≥ 3 months | Known peripheral neuropathy or injury to the path of the tibial nerve | Non-English speaking |
| | Demand-type cardiac pacemaker or implanted defibrillator | |

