3.4. Exclusion Criteria (table 1)

Patients on multiple bladder medications will be excluded for the rationale that they have a severely dysfunctional bladder that requires multiple bladder medications, likely having developed over many years. It is unlikely that TTNS alone can benefit this population and it would skew the results for efficacy.

Patients with known etiologies of incontinence other than SCI will be excluded.

Those patients with severe lower leg edema will be excluded because in our current trial, we have found that the electric current does not elicit toe flexion in those with extensive leg edema.

For electric stimulation, we exclude those that have an implanted cardiac device, cancer at the stimulation site, and those that we cannot elicit toe flexion in clinic.

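### If no contraction is seen, Section 5 allows maximal tolerable intensity; for enrolled subjects this can by inference apply only at home, and its only stated limits need sensation that entry does not require

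*Combined protocol and SAP*

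**What the plan says.** The TTNS protocol paragraph in Section 5 gives three rules for intensity. The default is: "The intensity level will be set to the amperage immediately under the threshold for motor contraction". The fallback is: "If there is not contraction seen, maximal tolerable intensity will be used". The third is a pain rule: "In addition, if the patient perceives pain, the intensity will be lowered until comfortable". The paragraph points to the inpatient study for the technique ("please refer to protocol HSC-MS-15-0806"). It gives no maximum amperage, and neither does any other section available here. Section 2.4 repeats the pain rule.

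On entry, Table 1 in Section 3.3 excludes people in whom toe or plantar flexion cannot be elicited in clinic. Section 6.4 says the same of the trial stimulation: "If no response or not tolerating electric stimulation, they will not be included in the study". Known peripheral neuropathy and injury along the tibial nerve are exclusions. Sensory loss from the cord injury itself is not, and neither is a complete injury.

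Table 2 in Section 4 lists daily stimulation under the home activities, and Aim 1 has it given by the subject or a caregiver.

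**The concern.** The default rule is safe without sensation, because a motor threshold can be seen. The fallback works differently. It applies when the visible sign is missing, and it replaces that sign with what the subject can tolerate. In someone who cannot feel the ankle, neither tolerance nor pain gives a signal, so the rule as written permits a current above the clinic setting. Toe flexion is also how Section 5 verifies electrode placement, so the current could go up just when placement is unconfirmed.

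Home safety is part of Primary Objective 1, and Section 9.1 names electrode burn as an event directly related to stimulation. The one numerical stopping rule covers urinary tract infection only.

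**Working it through.** The plan gives no figure to reproduce, so the check is to read the sections against each other.

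1. **When can the fallback apply?** It needs a session with no visible contraction. At the clinic trial, that result leads to exclusion (Section 3.3, Table 1; Section 6.4). For an enrolled subject, only later sessions remain, and Table 2 places those at home. Section 5 does not itself mention home; this step is inferred.

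2. **Could flexion be lost after entry?** Yes, but the documents do not say how often. Section 3.4 gives a mechanism: "Those patients with severe lower leg edema will be excluded because in our current trial" extensive swelling was found to stop the current from eliciting toe flexion. Table 1 words the exclusion as "2+ pitting edema that does not resolve", so swelling that comes and goes does not bar entry. The diary asks for the presence of toe flexion at each use, so the plan does not take it for granted.

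3. **What limits the current then?** Only tolerance and pain (Sections 5 and 2.4).

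4. **Does entry ensure that those limits work?** No. No criterion asks for sensation at the electrode site. The documents do not say how many subjects will lack it.

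5. **Do the other safeguards cap the current?** The plan has several:
   - device training and weekly calls (6.4)
   - a diary with amperage, flexion, a pain score and an open field (5)
   - adverse event collection with burn grading (9.2)
   - a response to redness still present the next day (2.4)
   - intolerance as a reason to stop (3.5)

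   None sets a ceiling. The pain score and intolerance again need sensation. Skin inspection is stated only for the clinic trial session (Section 6).

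6. **Would capping only the treatment current be enough?** No. Treatment current sits just below motor threshold, so a check for flexion must go above it. A cap that starts only after flexion has failed leaves the upward search unlimited. The search needs its own ceiling, and the natural one is the motor-threshold amperage measured in clinic.

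Arithmetic for the added burden, assuming 10 to 30 seconds per skin check:
- 4 weeks × 7 days = 28 checks
- 28 × 10 s = 280 s, about 4.7 minutes
- 28 × 30 s = 840 s = 14 minutes
- Stimulation time for comparison: 28 × 30 min = 840 min = 14 hours

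**The case against.** The strongest reply is that the home scenario comes from the reader and not from the plan. The fallback stands in a paragraph that refers to the inpatient protocol, and it may be inpatient text that was never meant for home use. This is a fair limit on the claim. It does not remove the problem: if the sentence was carried over, the only sessions it can still govern for enrolled subjects are the home ones.

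Second, a cap may exist where one would expect it: in the inpatient protocol, in the home directions (written, oral or video), in the diary or case report form listed as appendices, or in the device's own output limit. None of these was available. A reader might infer that subjects go home with no ceiling on the current at all. The documents do not support that; they show only that no ceiling is stated in this text.

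Third, the inpatient experience is reassuring. Section 1 reports 12 subjects (11 completed, 1 ongoing) with complete and incomplete injuries and no related adverse events, including skin irritation. Section 3.4 suggests that absent flexion had been met in the ongoing trial. This stands as reassurance. But those were inpatient sessions, and the text does not say whether the fallback was ever used. It is also tempting to turn zero events in 12 into an upper bound on risk. Such a bound would describe any related event in inpatients, not burns from the fallback at home, so it should not be offered as the size of this risk.

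Fourth, the evidence on sensation is indirect. Section 3.2 does expect tetraplegia ("Those with tetraplegia will unlikely have the ability to sign and we will have a 3rd party attest to the consent"), but that passage concerns the ability to sign, not feeling at the ankle. What stands is only that entry does not require sensation.

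**Conclusion.** The point holds as a minor safety correction. As written, the fallback is unsafe for a subject who cannot feel the site, because both of its stated limits rely on sensation. The default rule is not affected.

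The conclusion rests on the inference that the fallback can act only at home for enrolled subjects, and on no cap being stated in material that was not available. The risk is unquantified: the documents do not give the frequency of lost flexion, the number of subjects without sensation, or the device's maximum output. Harm would need lost flexion, lost sensation and a current raised above the clinic setting together. That is why the point is minor; the change is worth making because it is cheap and home safety is a primary objective.

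**What to change.** At the clinic trial, record two values for each subject: the motor-threshold amperage and the treatment amperage just below it. Write both on the home instructions. Replace the fallback sentence in Section 5 with:

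> At home, do not raise the current above the clinic motor-threshold amperage when checking for toe flexion. If flexion is not seen at that level, check for leg swelling and reposition the electrodes once; if it is still absent, treat at no more than the clinic treatment amperage and call the study team the same day.

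Unless the diary already has one, add a yes/no box for a look at the skin under both electrodes after removal, by the subject or caregiver. If a cap already stands in the home directions or the inpatient protocol, Section 5 needs only to state it, provided that it also limits the search for flexion.

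The cost is one replaced sentence, two numbers on the instruction sheet and 28 ticks per subject: about 5 to 14 minutes over four weeks on the assumed time per check, against 14 hours of stimulation. There are no extra visits. The downsides are possible under-dosing on days when flexion is absent, occasional unscheduled calls, and a slightly heavier diary, which matters a little because compliance is also a primary objective.

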1.2. Rationale and justification for the Study

We have selected a neuromodulation technique, TTNS, that has been used safely in chronic SCI with good results for improving quality of life and bladder parameters and have developed a protocol for home use.

Specific Aim 1: **Determine the safety, feasibility, and compliance of a daily home TTNS protocol in chronic SCI provided by self or caregiver for 4 weeks.**

Hypothesis 1.1: TTNS at home is safe and feasible with high compliance.

Hypothesis 1.2: TTNS protocol will demonstrate overall satisfaction as a neurogenic bladder treatment option based on survey questionnaire.

Specific Aim 2. **Determine the efficacy of a 4 week TTNS protocol.**

Hypothesis 2.1: Incontinence quality of life scores and frequency of incontinence will improve with TTNS compared to their baseline.

Hypothesis 2.2: Frequency of catheterization and volumes voided will improve with TTNS compared to baseline measurements.

Hypothesis 2.3: Anticholinergic-related side effects will improve with TTNS after discontinuation of bladder medications

a. Rationale for the Study Purpose

Neuromodulation techniques have been safely used for improving neurogenic bladder in chronic SCI for many years. However, bladder neuromodulation is only being performed in the clinic setting requiring frequent visits, limiting its use in a population known to have high healthcare costs and barriers to accessing medical care. Based on our experience, we believe we can develop a home-based protocol.

Gaps in the knowledge which we intend to fill are:

- 1) Safety, feasibility, and compliance of a home TTNS protocol in chronic SCI.
- 2) Efficacy of a 4-week TTNS protocol in SCI based on the Incontinence Quality of Life (I-QOL), which will provide effect size to power future studies.

b. Rationale for Doses Selected

Based upon an extensive review of the literature on neuromodulation of neurogenic bladder and the clinical experience of the mentorship team, we believe a TTNS protocol over a 4 week period will improve continence. Tibial nerve stimulation protocols use submotor current intensity with a duration of 200 μ s and frequency of 10Hz.^{13,14} Increasing the treatment frequency dramatically shortens the time required for response while maintaining efficacy, varying from 6-12 sessions.¹⁴

c. Rationale for Study Population

Participants will include consecutive SCI subjects at the SCI clinic who meet the I/E criteria (Table 1) and consent to the protocol.

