7.1. Trial Product (s)

The Stambil + is a class II medical device that requires a prescription for use. It is a multifunction electrotherapy device currently used at TIRR Memorial Hermann for the purpose of motor and sensory recovery in people with paralysis. It has the ability to provide conventional neuromuscular electric stimulation (NMES), transcutaneous electric nerve stimulation (TENS) and Pulsed Galvanic Stimulation electrotherapy. The device has wide-ranging capability and programmability, with stimulation and wave parameters adjusted for the proposed study purpose. The FDA Approved indications for the Empi Continuum are:

As an NMES device, indications are for the following conditions:

- Retarding or preventing disuse atrophy
- Maintaining or increasing range of motion
- Re-educating muscles
- Relaxation of muscle spasms
- Increasing local blood circulation
- Prevention of venous thrombosis of the calf muscles immediately after surgery

As a TENS device, indications are for the following conditions:

- Symptomatic relief and management of chronic, intractable pain
- Adjunctive treatment for post-surgical and post-trauma acute pain
- Relief of pain associated with arthritis

As a Pulsed Current device, indications are for the following conditions:

- Reduction of edema (under negative electrode)
- Reduction of muscle spasm
- Influencing local blood circulation (under negative electrode)
- Retardation or prevention of disuse atrophy
- Facilitation of voluntary motor function
- Maintenance of increase of range of motion

As a functional electrical stimulation (FES) device, the indications for the following condition:

- Stimulation of the leg and ankle muscles of partially paralyzed patients to provide flexion of the foot, thus improving the patient's gait

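### The dose sections pair 10 Hz with a 200 ms pulse, which cannot fit a 100 ms cycle; section 1.2b gives 200 μs, the only stated width that works

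*Combined protocol and SAP*

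**What the plan says.** Four places in the protocol state the stimulation parameters.

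- Section 5 (Study Design, TTNS protocol): "Stimulation frequency of 10 Hz and pulse width of 200ms in continuous mode will be used", citing references 13 and 14.
- Section 6.4 (Study Visits and Procedures): "stimulation frequency of 10 Hz and pulse width of 200ms in continuous mode for 30 minutes daily".
- Section 8.1 (Rationale for Selection of Dose): the same sentence as section 5, again citing references 13 and 14.
- Section 1.2b (Rationale for Doses Selected): "Tibial nerve stimulation protocols use submotor current intensity with a duration of 200 μ s and frequency of 10Hz", also citing references 13 and 14.

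Two other statements bear on the point. Section 5 opens its description with a pointer to the inpatient study, "TTNS protocol: (please refer to protocol HSC-MS-15-0806", which is not among the documents. Section 7.1 says the stimulator is a multifunction programmable unit, "with stimulation and wave parameters adjusted for the proposed study purpose".

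**The concern.** All four places agree on 10 Hz but disagree on the unit of the pulse width. The three that use milliseconds describe a waveform in which each pulse lasts longer than the interval before the next one starts.

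Sections 5 and 6.4 are where a reader would look for the settings. Stimulation is the study's only device intervention, and participants or caregivers deliver it at home. Anyone programming the unit from those sections meets an instruction that cannot be carried out. They must then take the width from the background rationale, look it up in the inpatient protocol, or lower the frequency.

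The record kept at home would not settle which was done. The diary entry for stimulation in section 5 covers "use of TTNS with amperage and presence of toe flexion, and pain score 0-10"; pulse width is not listed. Because the pilot is meant to supply an effect size for a larger trial, the dose behind that effect should be stated in a form that others can reproduce.

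**Working it through.** **Inputs**

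- Frequency f = 10 Hz (sections 1.2b, 5, 6.4 and 8.1).
- Pulse width w = 200 ms = 0.2 s (sections 5, 6.4 and 8.1), or 200 μs = 0.0002 s (section 1.2b).
- Session length = 30 min = 1,800 s (section 6.4).

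**Formulas**

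- Cycle length T = 1/f.
- Share of the cycle taken by the pulse = w/T, which must be below 1.
- Pulses per session = f × session length.
- Pulse time per session = pulses × w.
- Upper limit on frequency for a given width = 1/w.

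**Common values**

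- T = 1/10 s = 0.1 s = 100 ms.
- Pulses per session = 10 × 1,800 = 18,000.

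**Results**

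| Quantity | w = 200 ms | w = 200 μs |
|---|---|---|
| Share of cycle, w/T | 0.2/0.1 = 200% | 0.0002/0.1 = 0.2% |
| Share if each cycle has two phases of that width | 400% | 0.4% |
| Pulse time in a session | 18,000 × 0.2 = 3,600 s | 18,000 × 0.0002 = 3.6 s |
| Compared with the 1,800 s session | twice the session | fits |
| Upper limit on frequency, 1/w | 5 Hz | 5,000 Hz |

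The session totals restate the cycle result on a longer scale and are not separate evidence. At exactly 5 Hz a 200 ms pulse fills the whole cycle with no gap, so separate pulses of that width need a frequency below 5 Hz, less than half the stated rate.

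**Which element is wrong.** The frequency is 10 Hz in all four places; only the unit of the width varies. Changing the unit to μs makes all four statements agree. Keeping 200 ms would mean changing the frequency everywhere and would still contradict section 1.2b. The ratio of the two widths is 0.2/0.0002 = 1,000, as expected if milli was written for micro.

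The three millisecond statements are worded almost identically and may be one phrase reused, so they do not count as three independent confirmations.

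**The case against.** The arithmetic is not in dispute. The case on the other side is about cause and consequence.

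*It may be a PDF-reading fault.* A μ read as m would produce exactly this text. The symbol did survive in section 1.2b, but there it is set apart by a space, whereas the other three places show no space. The characters may be set differently, so success in one place says little about the others. A phrase pasted three times could also be misread three times. This stands as a reason to look at the original page first. It does not remove the contradiction in the text as supplied.

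*The error reveals itself and the answer is at hand.* An impossible pair cannot be followed silently. The feasible width is in section 1.2b, and section 5 points to an inpatient protocol already in use, which 11 of 12 participants had completed with no directly related adverse events. Trained staff run the clinic trial of stimulation, and participants receive directions there. All of this makes a wrong dose at home less likely, and nothing in the documents shows that one would occur. But this protocol restates the settings rather than leaving them to the cross-reference, and a cross-reference does not correct a conflicting statement.

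*The diary need not record a fixed setting.* This is fair. Amperage varies by session and pulse width should not, so its absence is no fault in the diary. The narrower point remains that those entries could not confirm the width used.

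*Section 1.2b describes general practice and its sources cannot be checked.* Also fair: that section reports what such protocols use, and the reference list in the public copy stops at item 6. The 200 μs value is therefore the only feasible one stated, not one verified against its sources.

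**Conclusion.** The concern holds. As written, the dose in sections 5, 6.4 and 8.1 is impossible: the pulse is twice as long as the cycle. The only other width in the document, 200 μs in section 1.2b, is feasible at 0.2% of the cycle and differs by a factor of 1,000.

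The impossibility needs no assumption beyond the stated frequency and width. That 200 μs is the intended value is an inference from section 1.2b and the constant 10 Hz. That the slip lies in the protocol and not in the extracted text depends on the original PDF.

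The error should be fixed because it sits in the operative dose text for a device used at home. Its reach is limited: the sample size, the UTI stopping rule and the planned analyses do not depend on it.

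**What to change.** 1. Check the original PDF to confirm that the three sections print ms.
2. Confirm the pulse width in protocol HSC-MS-15-0806 and on the device as programmed for this study.
3. If both support it, change ms to μs in sections 5, 6.4 and 8.1, so that each gives 10 Hz with a pulse width of 200 μs, in line with section 1.2b.
4. If any written, oral or video instruction for participants states a pulse width, make it match.

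The cost is a unit correction in three places and one check against the inpatient protocol and the device settings. The design, sample size and analysis do not change.
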